10.6.4 Analysis Methods

Time-to-Event Endpoints

For the time-to-event endpoints, the Kaplan-Meier estimates of the survival function will be calculated and graphically presented. The stratified log-rank test will be performed to evaluate treatment efficacy. The experimental arm will be declared superior if the 2-sided p-value from the stratified log-rank test is less than or equal to the desired significance level in favor of the experimental arm. The un-stratified log-rank test will be performed as sensitivity analysis.

Hazard ratio with two-sided 95% confidence interval (CI) will be estimated using the Cox proportional hazards model.

Binary Endpoints

The binary endpoints such as IOR will be summarized in frequency and percentage. The stratified Cochran-Mantel-Haenszel (CMH) test will be performed to evaluate treatment efficacy. The unstratified CMH test will be performed as sensitivity analysis.

10.7 Safety Analysis

Safety analyses will be based on all subjects in the safety population, and will be analyzed by the induction period, maintenance period, and follow-up period.

Study drug exposure will be summarized, including duration of study drug, total dose taken, and dose reductions.

Adverse events, vital sign measurements, clinical laboratory measurements, and concomitant medications will be summarized.

AEs will be coded according to Medical Dictionary for Drug Regulatory Activities (MedDRA) and classified using the National Cancer Institute Common Terminology Criteria for Adverse Events (CTCAE version 4.03, except for tumor flare, which will be assessed using version 3.0). The incidence rates of AEs will be tabulated by system organ class and preferred term. The incidence of AEs will also be tabulated by severity within each system organ class and preferred term. The most severe grade of each preferred term for a subject will be utilized for summaries of AEs by NCI CTCAE grade.

Subsets of AEs to be summarized include AEs, suspected treatment-related AEs, and AEs that result in withdrawal of investigational product.

AEs of interest include SPM, VTE, ATE, TLS, and TFR. All AEs with corresponding attributes will be displayed in a by-subject listing. Adverse events leading to death or to discontinuation from treatment, events classified as CTCAE Grade 3 or higher, suspected treatment-related events, and SAEs will also be displayed in separate by-subject listings.

Laboratory data will be summarized according to the CTCAE severity grade.

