This Phase 3b multicenter, randomized, open-label study will enroll subjects with relapsed/refractory follicular lymphoma grades 1-3b, transformed follicular lymphoma, marginal zone lymphoma or mantle cell lymphoma. All subjects enrolled will receive 12 cycles of lenalidomide plus rituximab induction therapy.

The study is designed to compare the efficacy and safety of two maintenance regimens following the induction therapy. Subjects who have stable disease (SD), partial response (PR), unconfirmed complete response (CRu) or complete response (CR) at the end of 12 cycles of induction therapy will be randomized to one of two maintenance arms: Arm A (experimental) or Arm B (control). Subjects randomized to Arm A will receive lenalidomide plus rituximab combination maintenance therapy (for 18 cycles) followed by optional lenalidomide single-agent maintenance (to progression). Subjects randomized to Arm B will receive rituximab single-agent maintenance (for 18 cycles).

Subjects will be stratified at time of randomization to the maintenance arm by histology, lines of anti-lymphoma therapy, and age.

The overall study design is described in Figure 1. The study is divided into a Screening Period, a Treatment Period (induction and maintenance), and a Follow-up Period. Approximately 500 subjects are planned to be enrolled.

Upon giving written informed consent, a subject will enter the Screening Period and undergo safety and other assessments to determine eligibility for the study. All Screening assessments must be completed within 28 days prior to the subject initiating induction therapy.

Subjects enter the Induction Treatment Period at the time they complete screening procedures and meet all eligibility criteria. Eligible subjects entering the Induction Treatment Phase will be enrolled using an Interactive Voice Response System (IVRS). The treatments will be given as described in detail in Section 8 and must begin no later than 1 week after enrollment in IVRS to receive induction therapy. Cycle length during induction and maintenance is 28 days.

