The End of Trial is defined as either the date of the last visit of the last subject to complete the study, or the date of receipt of the last data point from the last subject that is required for primary, secondary **analyses**, as pre-specified in the protocol and/or the Statistical Analysis Plan, whichever is the later date.

Study Treatments, please see Section 8.2 for details including dose adjustments for renal insufficiency

• Induction Period (12 Cycles)

Lenalidomide 20 mg once daily on Days 1 to 21 of every 28-day Cycle **AND** rituximab 375 mg/m² intra-venous (IV) every week in Cycle 1 (Days 1, 8, 15, and 22) and Day 1 of every other Cycle (Cycle 3, 5, 7, 9, 11)

Followed by Maintenance Period

• Arm A (Experimental arm): Lenalidomide + rituximab (Maintenance) followed by optional lenalidomide (Maintenance)

- Maintenance Period (18 Cycles)

Lenalidomide 10 mg once daily on Days 1 to 21 of every 28-day Cycle (Cycle 13 through 30) **AND** rituximab 375 mg/m² IV on Day 1 of every other Cycle up to Cycle 30 (Cycles 13, 15, 17, 19, 21, 23, 25, 27, 29).

Followed by

Optional Maintenance Period (up to PD)

Lenalidomide 10 mg once daily on Days 1 to 21 of every 28-day Cycle. This treatment will be at the discretion of the subject and/or the investigator.

VERSUS

- Arm B (Control arm): Rituximab (Maintenance)
 - Maintenance Period (18 Cycles)

Rituximab 375 mg/m2 IV on Day 1 of every other Cycle up to Cycle 30 (Cycles 13, 15, 17, 19, 21, 23, 25, 27, 29)

Overview of Efficacy Assessments

The International Working Group (IWG) 1999 response criteria (Cheson, 1999) for malignant lymphoma, modified to allow the inclusion of extranodal disease as measurable disease will be utilized for efficacy determination to assess response and progression. In addition to CT/MRI scan to assess disease, subjects with MZL involving the gastric area will undergo endoscopy as part of the response assessment.

The efficacy endpoints include:

- 1) Progression Free Survival (PFS)
- 2) Overall Survival (OS)
- 3) Improvement of Response (IOR)
- 4) Overall response rate (ORR) including partial response (PR), complete response (CR)/complete response unconfirmed (CRu) and CR/CRu rate (CRR)
- 5) Duration of response (DOR), duration of CR/CRu (DOCR)
- 6) Time to next anti-lymphoma treatment (TTNLT)
- 7) Time to histological transformation (TTHT)

Overview of Safety Assessments

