4.1.4 Randomization to Maintenance Treatment Period

After 12 cycles of lenalidomide plus rituximab induction therapy, subjects achieving CR/CRu, PR or having SD will be randomized to enter the maintenance period. During the maintenance period, subjects randomized to Arm B will receive rituximab (only) administered for 18 Cycles. Subjects randomized to Arm A will receive lenalidomide plus rituximab treatment for 18 Cycles and then lenalidomide until relapse or progression of disease. Lenalidomide (only) treatment in Arm A will be given per subject and/or physician discretion as described in detail in Section 8 and must begin no later than 1 week after the last cycle of rituximab plus lenalidomide. Subjects randomized under previous protocol (version 16 January 2014) who achieve a response of SD or better at the end of the Induction Treatment Period will remain in their originally assigned arm of maintenance therapy.

All subjects (in both Induction and Maintenance Treatment Periods) receive treatment as described unless they withdraw consent from treatment, experience unacceptable toxicities or have disease progression. Once subjects discontinue or complete treatment, they enter the follow-up period. All enrolled subjects will be followed for disease progression using the schedule described in Table 1. Subjects who progress before the end of planned treatment will enter the Follow-up Period. Determination of disease progression will be based on investigator assessment. All subjects who discontinue the protocol-specified treatment early for any reason without documented evidence of disease progression will also be followed in the Follow-up Period.

All subjects who will be on treatment upon reaching 5 years after the last subject has initiated induction therapy will continue the treatment and will be followed up for safety purposes only.

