4.1.5 Follow-up Period

Upon completion or discontinuation of the protocol-specified treatment, subjects will enter the Follow-up Period. In the Follow-up Period, all subjects will be followed for survival, time to next lymphoma treatment, and SPMs for 5 years after the last subject has initiated induction therapy unless they withdraw consent from the study, die or are lost to follow-up. Subjects whose disease has not yet progressed will also be followed for disease progression.

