5 TABLE OF EVENTS

		E				Induc	tion Pe	riod			Maintena nce Period	At 3 cycles (84 days after		Follo	ow-up	
PROCEDURE ^a	Screening Period	Every Cycle Day 1 Induction & Maintenance Periods (± 3 days)	C	ycle 1	l	Cycles 2 & 3	Cycles 3, 5, 7, 9 & 11	Cycles 5 & 9	Cycle 7	Cycle 10	Cycles 13, 15, 17, 19, 21, 23, 25, 27 & 29	At 6 cycles (168 days after C1D1)(±2 weeks)		If no PD then follow the CT		Ŧ
	Days -28 to -1	Up to PD for Arm A Or up to 30 cycles for Arm B	Day 1 (± 3 days)	Day 8 & 15 (± 1 day)	Day 22	Day 15 (± 1 day)	Day 1	Day 1 (± 3 days)	Day 1 (± 3 days)	Day 1 (± 3 days)	Day 1 (± 3 days)	Every 6 cycles (168 days) (±2 weeks) up to 5 years then Annually (± 3 weeks) ^b	At Treatment Discontinu ation/ Completio n	scan assessment schedule ^b		
Informed Consent	Х	-	-	-	-	-	-	-	-	-	-	-	-	-	-	
Inclusion/Exclusion Criteria	X	-	-	-	-	-	-	-	-	-	-	-	-	-	-	-
Demographic Data	Х	-	-	-	-	-	-	-	-	-	-	-	-	-	-	-
Lymphoma and Complete Medical History	х	-	-	-	-	-	-	-	-	-	-	-	-	-	-	-
Central Nervous System Lymphoma Evaluation	х	-	-	-	-	-	-	-	-	-	-	-	-	-	-	-
Creatinine Clearance (Cockcroft-Gault Estimation)	х	-	-	-	-	-	-	-	-	-	-	-	-	-	-	-
12-Lead Electrocardiogram	Х	-	-	-	-	-	-	-	-	-	-	-	-	-	-	-
HBV Screening ^c	Х	-	-	-	-	-	-	-	-	-	-	-	-	-	-	-

		E				Induc	tion Pe	riod			Maintena nce Period	At 3 cycles (84 days after		Follo	ow-up	
PROCEDURE ^a	Screening Period	Cycle Day 1 Induction & Maintenance Periods (± 3 days)		Cycle 1	L	Cycles 2 & 3	Cycles 3, 5, 7, 9 & 11	Cycles 5 & 9	Cycle 7	Cycle 10	Cycles 13, 15, 17, 19, 21, 23, 25, 27 & 29	At 6 cycles (168 days after C1D1)(±2 weeks)		If no PD then follow the CT		Ŧ
	Days -28 to -1	Up to PD for Arm A Or up to 30 cycles for Arm B	Day 1 (± 3 days)	Day 8 & 15 (± 1 day)	Day 22	Day 15 (± 1 day)	Day 1	Day 1 (± 3 days)	Day 1 (± 3 days)	Day 1 (± 3 days)	Day 1 (± 3 days)	Every 6 cycles (168 days) (±2 weeks) up to 5 years then Annually (± 3 weeks) ^b	At Treatment Discontinu ation/ Completio n	scan assessment schedule ^b		
Eastern Cooperative Oncology Group (ECOG) Performance Status	X	-	-	-	_	-	-	-	-	-	-	-	X	-	-	-
B Symptoms	Х	-	-	-	-	-	-	-	-	-	-	-	Х	-	-	-
Vitals Signs	X	X	-	-	-	-	-	-	-	-	-	-	X	-	-	-
Hematology Laboratory Tests ^g	X	Х	-	x	-	X	-	-	-	-	-	-	Х	-	-	-
Serum Chemistry Laboratory Tests ^g	X	Х	-	x	-	X	-	-	-	-	-	-	X	-	-	-
Thyroid Stimulating Hormone ^{g,n} (TSH)	X	-	-	-	-	-	-	-	-	-	-	-	х	-	-	-
Tumor Flare and Tumor Lysis Assessments ^h	-	-	X	x	-	-	-	-	-	-	-	-	-	-	-	-

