8.2 Treatment Administration and Schedule

Eligible subjects entering the Induction Treatment Phase will be enrolled using an Interactive Voice Response System (IVRS). Subjects entering the Maintenance Phase will be randomized using the IVRS into one of two arms (experimental or control) in a 1:1 ratio. Randomization will be stratified as described in Section 8.3. Subjects randomized under previous protocol (version 16 January 2014) who achieve a response of SD or better at the end of the Induction Treatment Period will remain in their originally assigned arm of maintenance therapy.

Study Treatments, please see Sections 8.2.1 and 8.2.2 for details

• Induction Period (12 Cycles)

Lenalidomide 20 mg (10 mg if creatinine clearance \geq 30 mL/min but < 60 mL/min) once daily on Days 1 to 21 of every 28-day Cycle for Cycles 1 to 12 **AND** rituximab 375 mg/m² every week in Cycle 1 (Days 1, 8, 15, and 22) and Day 1 of every 28-day Cycle for Cycles 3, 5, 7, 9, and 11

Followed by Maintenance Period

- Arm A (Experimental arm): Lenalidomide + rituximab (Maintenance) followed by optional lenalidomide (Maintenance)
 - Maintenance Period (18 Cycles)

Lenalidomide 10 mg once daily on Days 1 to 21 of every 28-day Cycle for Cycles 13 to 30 AND rituximab 375 mg/m2 on Day 1 of every 28-day Cycle for Cycles 13, 15, 17, 19, 21, 23, 25, 27, and 29

Followed by

- Optional Maintenance Period (up to PD)

Lenalidomide 10 mg once daily on Days 1 to 21 of every 28-day Cycle up to PD. This treatment will be at the discretion of the subject and the investigator.

VERSUS

• Arm B (Control arm): Rituximab (Maintenance)

Maintenance Period (18 Cycles)
 Rituximab 375 mg/m2 on Day 1 of every 28-day Cycle for Cycles 13, 15, 17, 19, 21, 23, 25, 27, and 29

Induction treatment must begin no later than 1 week after enrollment in IVRS to receive induction therapy. The Treatment Period for each subject starts with first intake of study drug, which is defined as Day 1 of Cycle 1.

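### Crude adverse-event percentages by maintenance period compare arms observed for different lengths of time, and Section 10.7 names no time-at-risk method

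*Combined protocol and SAP*

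**What the plan says.** Section 2.2 makes the between-arm safety comparison a secondary objective and defines Arm A's regimen to include the optional single-agent phase. Section 10.7 says the safety analyses "will be analyzed by the induction period, maintenance period, and follow-up period" and that "The incidence rates of AEs will be tabulated by system organ class and preferred term". It summarises duration of study drug but does not connect that summary to the adverse-event tables. It names no person-time, time-to-first-event or fixed-window method.

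On where the optional phase belongs:

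- Section 4.1.4, describing the maintenance period, states: "Subjects randomized to Arm A will receive lenalidomide plus rituximab treatment for 18 Cycles and then lenalidomide until relapse or progression of disease".
- The Table 1 column for induction and maintenance visits runs "Up to PD for Arm A Or up to 30 cycles for Arm B".
- The Protocol Summary has only one treatment block: "The study is divided into a Screening Period, a Treatment Period (induction and maintenance), and a Follow-up Period".
- Section 4.1.5 opens follow-up only when treatment ends: "Upon completion or discontinuation of the protocol-specified treatment, subjects will enter the Follow-up Period".
- Section 8.2 and the Protocol Summary nevertheless list the phase under its own heading, "Optional Maintenance Period (up to PD", apart from the 18-cycle Maintenance Period.

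Sections 6.2.1 and 11.1 collect adverse events to 28 days after the last dose. Second primary malignancies, and later serious events suspected to be drug-related, are the exceptions. Section 8.1 counts both drugs as investigational product, so Arm B's window runs from its last rituximab dose.

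**The concern.** A crude percentage answers how many subjects had the event while being watched. That is a fair between-arm contrast of risk only if the watching time is similar. Here it depends on the arm: Arm B stops at a fixed cycle, and Arm A may continue to progression. A higher percentage in Arm A could reflect greater toxicity, longer collection or both, and the planned tables cannot separate these.

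At stake is the interpretation of a stated secondary objective, including the events of interest (venous and arterial thromboembolism among them). The primary PFS test is not affected. The sponsor has already recognised the asymmetry elsewhere: the amendment history explains that time to treatment failure was dropped as an endpoint because treatment durations differ between the maintenance arms.

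**Working it through.** **Scheduled windows.** The documents give no window length in days, so there is no plan figure to reproduce. Take Cycle 13 Day 1 as day 0. With 28-day cycles, Cycle c Day d falls on day (c − 13) × 28 + (d − 1).

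- Rituximab in both arms: "rituximab 375 mg/m2 on Day 1 of every 28-day Cycle for Cycles 13, 15, 17, 19, 21, 23, 25, 27, and 29". Arm B's last dose is Cycle 29 Day 1: 16 × 28 = 448. Window end: 448 + 28 = **476**.
- Arm A, 18 cycles only. Last lenalidomide dose is Cycle 30 Day 21: 17 × 28 + 20 = 496. Window end: 496 + 28 = **524**.
- Arm A, optional phase: starts Cycle 31 Day 1 (18 × 28 = 504) and ends 28 days after the last dose, so up to progression + 28 days.

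The gap without the optional phase is 524 − 476 = 48 days (524/476 = 1.10). With it, the gap is open-ended.

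**Effect on crude percentages (illustration).** The 5% annual dropout is from Section 10.3. All other inputs are assumptions: equal event hazard in both arms, 12-month risk 5–20%, median PFS 24–60 months, observation capped at 36–60 months, and a hazard either constant or 3 or 10 times higher in the first 3 months of maintenance.

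Stopping hazard: μ = ln 2/(median PFS in years) − ln 0.95. Each window is min(stop, T) + 28 days, where T is 448 days (B), 496 days (A, declines) or the cap (A, opts in). For a constant event hazard λ:

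P(T) = 1 − e^(−28λ/365.25) × [ μ/(μ+λ) × (1 − e^(−(μ+λ)T)) + e^(−(μ+λ)T) ]

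Base case (12-month risk 10%, median PFS 36 months, cap 60 months): λ = −ln 0.90 = 0.105 per year; μ = 0.231 + 0.051 = 0.282 per year.

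- B, T = 448/365.25 = 1.227 years: 11.0%.
- A declining, T = 496/365.25 = 1.358 years: 11.8%; ratio 1.08.
- A opting in, T = 5 years: 23.9%; ratio 2.17.
- A at 50% uptake: (11.8 + 23.9)/2 ≈ 17.9%; ratio 1.62.

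Mean windows are 1.11 years in B against 1.20, 1.98 and 2.76 years in A at 0%, 50% and 100% uptake.

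Crude A:B ratio over the assumed ranges, equal stopping in both arms:

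| Uptake | Constant hazard | 3× early | 10× early |
|---|---|---|---|
| 50% | 1.30–1.85 | 1.22–1.62 | 1.11–1.31 |
| 100% | 1.54–2.62 | 1.39–2.17 | 1.20–1.59 |

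With no uptake the ratio is 1.06–1.08 (constant) or 1.01–1.06 (front-loaded).

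If Arm A has 20–30% per year extra stopping, the ratio over all hazard shapes is 0.88–0.98 at 0% uptake, 0.94–1.16 at 25%, 1.00–1.36 at 50% and 1.04–1.77 at 100%.

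**Do the alternatives behave better?** Still with equal true hazards:

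- Cumulative incidence at day 476 gives 1.00 with equal stopping. With 20–30% extra stopping in Arm A and end of collection as a competing event, it gives 0.83–0.96. With end of collection as censoring it gives 1.00, but only because stopping was simulated as independent of event risk.
- Exposure-adjusted rate ratios at 100% uptake and equal stopping are 0.81–0.87 (3×) and 0.58–0.72 (10×), so they can favour the longer-treated arm.

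**The case against.** **The period is not really in doubt.** A reader might infer that the plan leaves optional-phase events with no home. The documents do not support that. Section 4.1.4 describes single-agent lenalidomide within the maintenance period, Table 1 runs Arm A to progression, and follow-up begins only after treatment ends. What stands is a labelling conflict with the separate heading in Section 8.2, which one sentence would settle. Settling it towards inclusion gives the larger imbalance.

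**The objective compares whole regimens.** More events because a regimen lasts longer is part of that comparison. This is right, and it is why the whole-regimen table should stay. But that table alone cannot show whether risk differs over the same span of time.

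**The 28-day tail may be tabulated as follow-up.** Section 10.7 does not say. If maintenance tables stopped at the last dose, the scheduled ends would be days 448 and 496. The gap would still be 48 days and the optional-phase difference would be unchanged.

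**The illustration rests on assumed inputs.** This stands. The documents give no uptake, no adverse-event hazard and no early-stopping rate by arm, and nothing on event timing in maintenance. The thromboembolism timing in Section 6.2.13.2 comes from chemotherapy for high-grade lymphoma and does not establish front-loading here. The extra-stopping cases let any stop close the window. Section 8.2.4.3 keeps rituximab going after lenalidomide is stopped for toxicity, so some such stops before Cycle 29 might not shorten it.

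**Some mitigation exists.** Exposure duration is summarised, events are listed by subject and no formal safety test is planned. These help a careful reader but do not give a comparison at equal time.

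**Conclusion.** The point holds as a worthwhile, inexpensive improvement to Section 10.7. For subjects who take the optional phase, Arm A's collection window can far exceed Arm B's roughly 476 days, and the planned crude percentages do not account for that. Under equal hazards and equal stopping the apparent ratio is about 1.1–1.9 at 50% uptake and 1.2–2.6 at 100%.

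Three stronger readings are not supported:

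- That the tables will necessarily overstate Arm A's toxicity. Extra stopping in Arm A can shrink the ratio or take it below 1.
- That the 48-day difference without the optional phase is itself a material bias. It moves the ratio by at most about 8% when stopping is equal.
- That second primary malignancies need a separate remedy. Their reporting already ends for both arms 5 years after the last subject starts induction, and a note that between-arm comparisons use that end is enough.

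The windows are scheduled values; delays and early stopping move them. The documents refer to a Statistical Analysis Plan, but no separate SAP safety text was supplied, so the conclusion is limited to Section 10.7 as it stands.

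**What to change.** In Section 10.7:

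1. State that the maintenance period includes Arm A's optional phase, and reconcile this with the headings in Section 8.2 and the Protocol Summary.
2. Keep the whole-regimen incidence table and print time at risk by arm beside it.
3. Add between-arm cumulative incidence of first event from the first maintenance dose for all adverse events, Grade 3 or higher events, serious events, and venous and arterial thromboembolism. Report it at a common time inside both scheduled windows, about day 476. That day is also Cycle 30 Day 1 ((30 − 13) × 28 = 476), a visit with a ±3-day window, so define the cut by onset date. Treat death as a competing event. State how end of collection is handled, as competing event or as censoring, with the other as a sensitivity analysis. Give exposure-adjusted rates as support only.
4. Tabulate later-onset events separately, including those in the optional phase, so that none is lost.

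If a separate SAP already does this, a cross-reference suffices.

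The cost is a few extra tables from dates already collected. The plan should name two drawbacks: exposure-adjusted rates can favour the longer-treated arm when events cluster early, and treating end of collection as a competing event can favour the arm with more early stopping.

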10.8 Interim Analysis

A formal interim analysis for futility only is planned to examine the overall response rate to induction therapy, which is defined as the proportion of subjects whose response at the end of induction period is at least PR (including CR, CRu and PR). It will be conducted with the first 50 efficacy evaluable subjects by the end of the Induction Period. Efficacy evaluable subjects are defined as subjects who have had the scheduled response assessment at 12 months, or progressed or died before the end of the Induction Treatment Period. If the lower limit of the 95% confidence interval for overall response rate during the induction period in these 50 subjects is less than 30% then the trial might be stopped for futility.

Since this interim analysis is only to evaluate the induction therapy, it has no impact on the number of events we need for the maintenance period, sample size, or alpha.

Considering the current PFS event rate and estimated timing of final analysis, one nonbinding interim analysis for patients in the maintenance phase is planned at 50% of information (95 PFS events) for both superiority and futility. The date of occurrence of the 95th PFS event will be used as data cut-off date for the analysis. This interim analysis will be conducted by an external independent statistician, while the study team will remain blinded.

The study may be stopped early for futility if the observed hazard ratio (HR) is > 1.154, based on Gamma (-8) family (Hwang, Shih, and DeCani, 1990), ie, in favor of the control arm, and/or if recommended by the DMC based on the safety profile of this combination regimen. The stopping boundary for superiority based on O'Brien Fleming Analog (Lan & DeMets, 1983) is hazard ratio ≤ 0.546 , if the observed HR cross the superiority boundary in favor of the proposed treatment, the trial may stop and claim the superiority. To ensure the overall 1-sided type 1 error remains at 0.025, an appropriate amount of alpha will be spent for the interim analysis.

The DMC will review the efficacy and safety data from these analyses and communicate recommendations to the sponsor who may use the recommendations in a risk/benefit analysis.

